## 13.4.3.2 Secondary Analyses

Secondary efficacy analyses will examine the effects of the treatment on changes observed in other efficacy measures (ie, CGI-S, ASHS, and SCARED). These analyses will model the overall or total scale scores and will employ the same general approach as for the primary analysis. All secondary efficacy measures will be treated as continuous measurement scales and analyzed by the ANOVA methods described above.

Results of the CGI-I assessment will also be dichotomized and presented for each week of treatment. CGI-I scores of 1 or 2 will be combined into a single group labelled "Improved" and scores of 3 to 7 will be combined and labelled "No Improvement." The observed proportions of "Improved" subjects will be compared between treatment groups at each week of the study.

In addition, analysis of the weekly results from ADHD-RS-5 and CGI-I will be evaluated for evidence of trend over time. This analysis will employ a linear mixed-effects model with repeated measures on each subject. Terms for the model will be selected as described for the primary analysis.

Secondary analyses will focus on the ITT Population. However, analyses of the PP Population may be performed if warranted by the data.

# 13.4.4 Safety and Tolerability Analyses

Safety analyses will be conducted using data from the Safety Population (as defined in Section 13.3). Safety variables include treatment-emergent adverse events (TEAEs), clinical laboratory values, vital signs, ECG results, C-SSRS, and physical examination results. No formal inferential analyses will be conducted for safety variables, unless otherwise noted.

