# 13.3 Analysis Populations

The design of this study yields 3 main populations of scientific interest.

The Safety Population will consist of all subjects who are randomized into the study and receive any amount of IP.

The Intent-to-Treat (ITT) Population will be composed of all subjects who are randomized into the study.

The occurrence of significant protocol deviations may lead to the exclusion of some subjects from specific analyses, thereby yielding a Per-protocol (PP) Population.

Specific subgroups of these populations may also be evaluated as warranted by the experimental results.

Membership in the analysis populations will be determined prior to unblinding.

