5 ANALYSIS POPULATIONS

The following analysis populations are planned for this study:

- Safety Population (SAFETY): The Safety Population includes all subjects who are randomized into the study and receive any amount of Investigational Product (IP).
- **Intent-To-Treat Population (ITT):** The ITT Population includes all subjects who are randomized into the study.
- **Per-Protocol Population (PP):** The PP Population includes all randomized subjects who do not have any significant protocol deviations defined as a major protocol deviation. Major protocol deviations are listed in section 7 (below). Membership in the PP population will be determined by a blinded review of patient data prior to database lock.

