- SCARED Significant School Avoidance is the summation of questions 2, 11, 17, and 36.
- SCARED Total Score is the summation of all 41 questions, each scored from 0 to 2 scale.
- C-SSRS Suicidal Ideation is an indicator of any subject who experience any one of the five suicidal ideation events at least once (Questions 4, 6, 8, 10, and 12)
- C-SSRS Suicidal Behavior is an indicator of any subject who experience any one of the suicidal behavior events at least once (Questions 22, 26, 29, 32, and 35)
- C-SSRS composite endpoint of Suicidal Ideation or Behavior is an indicator of any subject who experiences any one of the ten suicidal ideation or behavior events at least once.
- TEAE An AE is defined as treatment emergent if the first onset or worsening is after the first administration of IP (NFC-1 or placebo) and not more than 7 days after the last administration of IP
- For the tabulation of TEAE's that are related to study drug, these are defined as any TEAE which is determined by the investigator as 'possibly related' or 'related'.
- Post-Treatment AE is an AE that has started more than 7 days after last administration of IP.
- Prior medications are defined as medications or therapies initiated prior to date of first dose of IP and terminating prior to date of first dose of IP. Medications that are started prior to the date of first dose of IP and are continuing after the first dose of IP are considered to be both prior and concomitant medications
- Concomitant medication is defined as any medication a subject received concurrently with study treatment.
- Post-treatment medication is defined as any medication that has started more than 7 days after the last administration of IP.
- Compliance (Overall) = $(\sum (Individual Week Compliance) * (Time-Weight)) * 100. A subject is non-compliant if they take <math>< 80\%$ or > 120% of IP.
 - Individual Week Compliance is defined as the number of capsules taken at a particular week divided by the expected number of capsules taken at a particular week. Given that a subject will be dose optimized, the number of expected capsules will vary according to which dose the subject is currently on for each day.
 - Time-Weight is the fraction of \mathbf{x}/\mathbf{y} where \mathbf{x} is the number of days in the week the subject is expected to be on dose and \mathbf{y} is the whole treatment duration defined as first dose last dose + 1.

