9 SAFETY AND TOLERABILITY ANALYSIS

The analysis of safety assessments in this study will include summaries of the following categories of safety and tolerability data collected for each subject:

- Adverse Events
 - Summary of all Adverse Events
 - treatment-emergent adverse events (TEAEs), and serious adverse events (SAEs)
 - TEAEs leading to early termination
 - TEAEs by severity
 - TEAEs deemed related to the IP
 - TEAEs occurring in more than 5% of subjects
 - Post-treatment AEs
 - Any deaths
- Clinical Laboratory Investigations(chemistry, Hematology, Urinalysis)
- Vital Signs (systolic and diastolic blood pressure, pulse, respiratory rate, height, weight, and BMI)
- Electrocardiograms (ECG)
- C-SSRS Score
- Concomitant Medications
- Post-treatment Medications
- Study Drug Exposure and Treatment Compliance

All tabulations and summaries for these categories will be performed on the Safety population unless otherwise noted.

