9.2 Clinical Laboratory Evaluations

Descriptive summaries of actual (absolute) values and changes from baseline will be presented for Chemistry, Hematology, and Urinalysis analytes. These tables will be grouped by treatment group, and by visit. Summaries will be displayed in conventional units.

The number and proportion of subjects with clinical laboratory values below, within, or above normal ranges, at each study visit will be tabulated (shift tables) for each clinical laboratory analyte by treatment group. Normal ranges for lab results will be provided by the Central laboratory used in this study (i.e., Eurofins).

Laboratory values will be displayed in the data listings and those that are outside the normal range will be flagged, along with corresponding normal ranges.

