11.2 Planned Table Shells

Table	Table Title	Topline
14.1.1	Disposition of Study Population by Optimized Dose and Randomized Treatment (ITT Population)	х
14.1.2	Major Protocol Deviations (ITT Population)	
14.1.3	Demographics and Baseline Characteristics by Optimized Dose and Randomized Treatment (Safety Population)	х
14.1.4	Disease Characteristics at Baseline by Optimized Dose and Randomized Treatment (Safety Population)	х
14.1.5	Summary of Prior Medications by Randomized Treatment (Safety Population)	
14.2.1.1	Analysis of Change from Baseline in ADHD-RS-5: Total Score and Subscales, by Study Visit (ITT Population)	х
14.2.1.2	Summary of Change from Baseline in ADHD-RS-5 Score and Subscales by Actual Dose and Randomized Treatment, by Study Visit (ITT Population)	
14.2.2.1	Chi-Square Analysis of CGI-I Improvement, by Study Visit (ITT Population)	х
14.2.2.2	Summary of Categorical and Continuous CGI-I Scores by Randomized Treatment Group and Study Visit (ITT Population)	х
14.2.2.3	Summary of CGI-I Improvement by Optimized Dose and Randomized Treatment, by Study Visit (ITT Population)	
14.2.3.1	Chi-Square Analysis of CGI-S Improvement, by Study Visit (ITT Population)	
14.2.3.2	Summary of Categorical and Continuous CGI-S Scores by Randomized Treatment Group and Study Visit (ITT Population)	
14.2.3.3	Summary of CGI-S Improvement by Optimized Dose and Randomized Treatment, by Study Visit (ITT Population)	
14.2.4.1	Analysis of Change from Baseline in ASHS Total Score and Factors, by Study Visit (ITT Population)	
14.2.4.2	Summary of Change from Baseline in ASHS Total Score and Factors by Randomized Treatment, by Study Visit (ITT Population)	
14.2.5.1	Analysis of Change from Baseline in SCARED Score and Factors, by Study Visit (ITT Population)	
14.2.5.2	Summary of Change from Baseline in SCARED Score and Factors by Randomized Treatment, by Study Visit (ITT Population)	
14.2.6.1	Chi-Square Analysis of Response and Remission Criteria, at End of Study (ITT Population)	х
14.3.1.1	Summary of TEAEs by Dose at Onset (Safety Population)	
14.3.1.2	Incidence of TEAEs by Dose at Onset and Randomized Treatment (Safety Population)	х
14.3.1.3	Incidence of TEAEs occurring in more than 5% of subjects by Randomized Treatment (Safety Population)	

SAP FINAL Version 2.0

14.3.1.4	Incidence of Post-Treatment AE's by Randomized Treatment (Safety Population)	
14.3.1.5	Incidence of SAE's by Randomized Treatment (Safety Population)	

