14.3.1.6	Incidence of TEAEs Leading to Early Termination by Randomized Treatment (Safety Population)	
14.3.1.7	Incidence of Deaths by Randomized Treatment (Safety Population)	
14.3.1.8	Incidence of TEAEs by Relationship to Study Drug by Randomized Treatment (Safety Population)	
14.3.1.9	Incidence of TEAEs by Maximum Severity by Randomized Treatment (Safety Population)	
14.3.2	Summary of Exposure to Study Drug and Compliance by Actual Dose and Randomized Treatment (Safety Population)	
14.3.3.1	Summary of Clinical Laboratory Data: Clinical Chemistry by Randomized Treatment by Study Visit (Safety Population)	
14.3.3.2	Summary of Clinical Laboratory Data: Hematology by Randomized Treatment by Study Visit (Safety Population)	
14.3.3.3	Summary of Clinical Laboratory Data: Urinalysis by Randomized Treatment by Study Visit (Safety Population)	
14.3.3.4	Shifts from Baseline of Clinical Laboratory Data: Clinical Chemistry by Randomized Treatment (Safety Population)	
14.3.3.5	Shifts from Baseline of Clinical Laboratory Data: Hematology by Randomized Treatment (Safety Population)	
14.3.3.6	Shifts from Baseline of Clinical Laboratory Data: Urinalysis by Randomized Treatment (Safety Population)	
14.3.4.1	Summary of Vital Signs by Randomized Treatment by Study Visit (Safety Population)	
14.3.4.2	Potentially Clinically Important Vital Signs by Randomized Treatment (Safety Population)	
14.3.5.1	Incidence of Abnormal ECG Findings: based on Site Interpretations by Randomized Treatment by Study Visit (Safety Population)	
14.3.5.2	Incidence of Abnormal ECG Findings: based on Central Reading by Randomized Treatment by Study Visit (Safety Population)	
14.3.5.3	Potentially Clinically Important ECG Results by Randomized Treatment (Safety Population)	
14.3.6	Summary of C-SSRS Assessments by Randomized Treatment (Safety Population)	
14.3.7	Summary of Concomitant Medications by Randomized Treatment (Safety Population)	
14.3.8	Summary of Post-Treatment Medications by Randomized Treatment (Safety Population)	
14.3.8	Summary of Post-Treatment ineutcations by Randomized Treatment (Safety Population)	

Protocol: MDGN-NFC1-ADHD-201 SAP FINAL Version 2.0

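### Neither document has an as-treated rule for safety: 23 of 24 safety tables group by randomized treatment, so events in a placebo-randomized subject who took NFC-1 would count under placebo

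*Protocol*

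**What the plan says.** **Membership.** Protocol 13.3 says the Safety "Population will consist of all subjects who are randomized into the study and receive any amount of IP". SAP 5 agrees: "The Safety Population includes all subjects who are randomized into the study and receive any amount of Investigational Product (IP". IP covers both products. The treatment-emergent definition in SAP 6.3 counts from the "first administration of IP (NFC-1 or placebo", so a subject given the wrong product remains in the population.

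**Use.** Protocol 13.4.4 refers back to that definition and names no grouping variable: "Safety analyses will be conducted using data from the Safety Population (as defined in Section 13.3". SAP 9 says: "All tabulations and summaries for these categories will be performed on the Safety population unless otherwise noted".

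**Grouping in the SAP text.** SAP 9.2 is typical: "These tables will be grouped by treatment group, and by visit". The SAP text does not say whether treatment group means the treatment assigned or the treatment taken.

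**Grouping in the table list.** SAP 11.2 is explicit. Examples are Table 14.3.1.2, "Incidence of TEAEs by Dose at Onset and Randomized Treatment (Safety Population", and Table 14.3.1.8, "Incidence of TEAEs by Relationship to Study Drug by Randomized Treatment (Safety Population".

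Neither document contains a rule that assigns safety data to the treatment received, and SAP 10 (changes from planned analysis) does not raise the matter.

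**The concern.** Grouping by randomization protects the efficacy comparison. For safety, the question is what happened to subjects after they took the drug, and the study's second objective (Protocol 6) is safety data following exposure to NFC-1. Under the titles in SAP 11.2, an event in a placebo-randomized subject who took NFC-1 would be counted in the placebo column, which raises the placebo rate and lowers the NFC-1 rate. The reverse can also occur: a subject randomized to NFC-1 who took only placebo would stay in the NFC-1 denominator.

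Raw counts carry much of the weight here. There is no data safety monitoring board (Protocol 12), safety has no formal inference unless otherwise noted (Protocol 13.4.4), and psychosis and suicidal ideation are named as events of special interest (Protocol 11.3.1). With arms this small, one event on the wrong side can change how a rare finding is read.

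**Working it through.** The plan states no figure on this point, so there is none to reproduce. The check has three parts: a count of titles, an illustration of the effect, and a bound on how often the situation could arise.

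**1. Titles in the 14.3 series (SAP 11.2).**
- Adverse events, 14.3.1.1 to 14.3.1.9: 9 tables
- Exposure and compliance, 14.3.2: 1
- Laboratory, 14.3.3.1 to 14.3.3.6: 6
- Vital signs, 14.3.4.1 and 14.3.4.2: 2
- ECG, 14.3.5.1 to 14.3.5.3: 3
- C-SSRS, concomitant and post-treatment medications, 14.3.6 to 14.3.8: 3

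The total is 9 + 1 + 6 + 2 + 3 + 3 = 24. All carry Randomized Treatment except 14.3.1.1, so 23 of 24. Two of the 23 add an exposure key to the title: 14.3.1.2 (dose at onset) and 14.3.2 (actual dose).

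**2. Effect on the counts.** Input: about 45 subjects per arm (Protocol 7.1). Assumptions: *m* placebo-randomized subjects took NFC-1 and had the event, *a* subjects in the NFC-1 arm had it, and no other placebo subject did.
- As randomized: *a*/45 versus *m*/45
- As treated: (*a* + *m*)/(45 + *m*) versus 0/(45 − *m*)

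| m | a | As randomized, NFC-1 vs placebo | As treated, NFC-1 vs placebo |
|---|---|---|---|
| 1 | 0 | 0/45 (0%) vs 1/45 (2.2%) | 1/46 (2.2%) vs 0/44 (0%) |
| 1 | 2 | 2/45 (4.4%) vs 1/45 (2.2%) | 3/46 (6.5%) vs 0/44 (0%) |
| 2 | 2 | 2/45 (4.4%) vs 2/45 (4.4%) | 4/47 (8.5%) vs 0/43 (0%) |

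With *m* = 0 the two groupings are identical. In the second row the NFC-1 rate crosses the 5% threshold of Table 14.3.1.3 (4.4% to 6.5%). That matters only if the threshold is applied per arm, which the SAP does not say.

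**3. How often it could arise.** The schedule of events (Protocol 17.1) shows IP dispensed at Visits 2 to 7, six times. If any NFC-1 intake counts as NFC-1, a single wrong bottle changes the safety arm only of a placebo-randomized subject. The relevant number is therefore at most 45 × 6 = 270 dispensings, ignoring dropout. For a wrong-product rate *p* per dispensing, the chance of at least one error is 1 − (1 − *p*)^270:
- *p* = 0.05%: 12.6%
- *p* = 0.1%: 23.7%
- *p* = 0.5%: 74.2%

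These rates are pure assumptions, since neither document gives or implies one. The results are chances of a dispensing error, not of a misplaced adverse event, which also requires that the subject takes the product and has an event.

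**The case against.** The strongest objection is that nothing in the documents suggests anyone will take the wrong product. The IWRS randomizes subjects, assigns treatment numbers and manages dispensing (Protocol 9.4.1 and 17.1). The evidence is table titles, and SAP Appendix A calls the shells programming guidance that may be updated independently of the SAP. An error could also be found: investigational-product deviations are a listed category (SAP 7.2), and exposure, accountability, deviations and adverse events are all listed by subject. In a 90-subject study such a case could be footnoted.

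Most of this is fair and limits the size of the point. It does not remove it. The titles are the only place where either document fixes the grouping, and they fix it as randomized. A major deviation affects membership of the Per-Protocol Population (SAP 5), not the safety column. Listing 16.2.1.1 has a single treatment column, so a mismatch would not show there. A footnote written after the case is known would be a post-hoc decision about where an event belongs.

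A second objection is that an as-treated rule creates its own misplacement. A placebo subject given one wrong bottle at Visit 7 would have about five weeks of placebo-period data moved to NFC-1. This stands, and is why the rule for mixed exposure needs care.

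Three stronger readings are tempting and are not supported:
- *A misdispensed subject has no correct column in Table 14.3.1.2.* The shell has 100 mg, 200 mg, 400 mg, NFC-1 and Placebo columns. The fault is that the title does not say which key decides.
- *All safety tables are by randomized treatment.* Table 14.3.1.1, which includes serious events, discontinuations and deaths, is by dose at onset only.
- *Every dispensing in the study is at risk.* Counting 90 × 6 = 540 roughly doubles the exposure. An NFC-1-randomized subject given one wrong placebo bottle stays under NFC-1 if any NFC-1 intake decides the arm.

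**Conclusion.** The point holds as a gap in the plan, with a contingent effect. Membership is set by receipt of any IP, 23 of 24 safety tables group by randomized treatment, and no rule covers a subject whose received and assigned treatments differ. The plan as written would count such a subject's events under the assigned arm, against the purpose of the safety objective.

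The effect is nil unless a subject takes the wrong product. If one does and has an event, a 0 versus 1 split as randomized becomes 1 versus 0 as treated, assuming 45 per arm and no other cases. The documents do not support a claim that this has happened or is likely. The change is worth making because it costs little and has to be settled before unblinding to be free of hindsight.

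**What to change.** 1. State in SAP 5 and SAP 9 that Safety Population outputs group subjects by treatment actually received.
2. Fix, before unblinding, a rule for subjects who took both products. One option: any NFC-1 intake counts as NFC-1 in subject-level tables, while dose-at-onset tables assign each event to the product and dose being taken when it began.
3. Replace Randomized Treatment with Treatment Received in the 14.3 titles, keeping Dose at Onset in 14.3.1.2 and Actual Dose in 14.3.2. A blanket retitling that dropped those keys would lose planned groupings.
4. Flag in Listing 16.2.1.1 any subject whose randomized and received treatments differ.
5. Leave efficacy on the ITT Population, as randomized.

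The cost is a short SAP addition, revised titles, one variable derived from IWRS and accountability data, and one flag. The downside is small: under the option in item 2, a mixed-exposure subject's placebo-period events move to NFC-1 in the subject-level tables. The flag and subject listings make that visible.

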### 13.4.4.1 Adverse Events

Adverse events will be coded using the most recent version of the Medical Dictionary for Regulatory Activities (MedDRA). Treatment-emergent AEs will be summarized by system organ class (SOC) and preferred term. Treatment-emergent AEs will be presented as the number and proportion of subjects reporting each event. Similar summaries will be produced for post-treatment AEs, SAEs, AEs leading to termination, and AEs with at least a possible relationship to the IP. The intensity of AEs and the relationship to the IP will also be summarized for each SOC and preferred term.

### 13.4.4.2 Clinical Laboratory Evaluations

Descriptive summaries of actual (absolute) values and changes from baseline values will be presented by treatment group for each study visit.

The number of subjects with clinical laboratory values below, within, or above normal ranges, at each study visit will be tabulated (shift tables) for each clinical laboratory analyte by treatment group.

# 13.4.4.3 Vital Signs and Electrocardiograms

Vital signs (systolic and diastolic blood pressure, pulse, and respiratory rate), and ECG results will be summarized by visit and treatment group using appropriate descriptive statistics. The number and percentage of subjects with abnormal ECG findings will be summarized by treatment group for each study visit.

# 13.4.4.4 Columbia Suicide Severity Rating Scale

The C-SSRS score will be summarized by visit and treatment group using descriptive statistics.

# 13.4.4.5 Physical Examination Findings

The number and percentage of subjects with normal and abnormal findings in the complete physical examination will be displayed for each treatment group.

# 13.4.5 Interim Analysis

No interim analysis is planned for this study.

# 14. STUDY CONDUCT

Steps to ensure the accuracy and reliability of data include the selection of qualified investigators and appropriate study sites, review of protocol procedures with the investigator and associated personnel prior to the study, periodic monitoring visits, and meticulous data management.

# 14.1 Sponsor and Investigator Responsibilities

## 14.1.1 Sponsor Responsibilities

The sponsor is obligated to conduct the study in accordance with strict ethical principles (Section 15). The sponsor reserves the right to withdraw a subject from the study (Section 8.3), to terminate participation of a study site at any time (Section 14.7), and/or to discontinue the study (Section 14.6).

Medgenics agrees to provide the investigator with sufficient material and support to permit the investigator to conduct the study according to the study protocol.

## 14.1.2 Investigator Responsibilities

By signing the Investigator's Agreement in Section 17.2, the investigator indicates that she/he has carefully read the protocol, fully understands the requirements, and agrees to conduct the study in accordance with the procedures and requirements described in this protocol.

The investigator also agrees to conduct this study in accordance with all laws, regulations, and guidelines of the pertinent regulatory authorities, including and in accordance with the April 1996 International Conference on Harmonisation (ICH) Guidance for Industry E6 GCP and in agreement with the 1996 Version of the Declaration of Helsinki. While delegation of certain aspects of the study to subinvestigators and study coordinators is appropriate, the investigator will remain personally accountable for closely overseeing the study and for ensuring compliance with the protocol and all applicable regulations and guidelines. The investigator is responsible for maintaining a list of all persons that have been delegated study-related responsibilities (eg, subinvestigators and study coordinators) and their specific study-related duties.

Investigators should ensure that all persons who have been delegated study-related responsibilities are adequately qualified and informed about the protocol, IPs, and their specific duties within the context of the study. Investigators are responsible for providing Medgenics with documentation of the qualifications, GCP training, and research experience for themselves and their staff as required by the sponsor and the relevant governing authorities.

To ensure compliance with the guidelines, the study will be audited by an independent person. The investigator agrees, by written consent to this protocol, to cooperate fully with compliance checks by allowing access to all study documentation by authorized individuals.

